### 10.8.1 Unified Huntington's Disease Rating Scale

Summary statistics will be provided for each subtest of the UHDRS (TFC, motor, cognitive, independence, and functional assessments) by dose cohort and visit. A composite score of some or all of the components of the UHDRS may also be calculated. The change from baseline to the last measured time point will be determined. Individual patient data will be listed. Additional details on the statistical analysis of UHDRS data will be provided in the SAP.

## **10.8.2 Short Problem Behaviors Assessment**

Summary statistics will be provided for PBA-s data by dose cohort and visit. The change from baseline to the last measured time point will be determined. Individual patient data will be listed. Additional details on the statistical analysis of PBA-s data will be provided in the SAP.

## **10.9 SAFETY ANALYSES**

Safety data will be analyzed descriptively overall and by treatment group and dose cohort, and no formal statistical comparisons will be performed. Data from unscheduled visits (laboratory tests, vital signs, physical examinations, and ECGs) will not be included in the tables, but will be included in the by-patient listings.

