### **3 STUDY OBJECTIVES AND ENDPOINTS**

#### **3.1 STUDY OBJECTIVES**

##### **Primary Objective**

The primary objective of this study is to evaluate the safety and tolerability of WVE-120101 in patients with early manifest HD.

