  - h For female patients of childbearing potential, a negative serum pregnancy test must be documented at the Screening Visit. On dosing days, a negative urine pregnancy test must be documented predose.
  - i Vital signs include blood pressure, pulse, temperature, weight, and height. On dosing days blood pressure and pulse will be measured at the following time points:  $\leq 30$  minutes predose and 1, 2, and 4 hours ( $\pm 15$  minutes) postdose. Sentinel patients will also have blood pressure and pulse measured 12 hours ( $\pm 2$  hours), 24 and 48 hours ( $\pm 4$  hours) postdose. Weight and temperature will only be measured predose on dosing days. Height will be measured at baseline only. Blood pressure (systolic and diastolic), temperature, and pulse should be measured after patient has been resting quietly for  $\geq 3$  minutes.
  - j Electrocardiogram recordings will be obtained in triplicate in the supine position after the patient has rested comfortably for  $\geq 5$  minutes.
  - k Clinical laboratory safety testing, including clinical chemistry, hematology, and urinalysis. Within 1 week prior to lumbar puncture, a blood sample will be tested to confirm platelet count and prothrombin clotting time. Clinical laboratory safety testing will be performed predose on all dosing days. On Day 1 only, samples for clinical chemistry and hematology measures (CBC, complement, and fibrinogen only) will also be collected at 1 and 4 hours ( $\pm 15$  minutes), and 24 hours ( $\pm 4$  hours) postdose, and for sentinel patients only, 48 hours ( $\pm 4$  hours). On all non-dosing days, clinical laboratory safety testing will be performed just once. On Day 196, only platelet count and prothrombin clotting time need to be assessed (prior to CSF sample). Urinalysis will be performed predose on all dosing days, and once on all other days noted.
  - l Blood samples for the Prescreening assays to determine eligibility.

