### **10.9.2 Clinical Laboratory Evaluations**

Laboratory test values and changes from baseline over time will be summarized for each continuous clinical laboratory parameter. Shift tables showing the pattern of change from baseline to postbaseline visit(s) will be presented.

All laboratory data will be presented by patient in data listings. For hematology and chemistry laboratory data, the laboratory normal ranges will be provided, and individual abnormal laboratory values will be flagged and clinical significance will be indicated. A separate listing of only clinically significant hematology and chemistry findings will be provided.

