### **10.9.3 Vital Signs**

The actual value and change from baseline to each postbaseline assessment will be summarized for vital signs (systolic and diastolic blood pressure, pulse rates, and weight). Height and body mass index will also be presented. Vital signs measurements will be presented by patient in data listings.

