#### **10.9.4 Electrocardiogram**

Summary statistics will be provided for ECG data by dose cohort and visit. Individual patient data will be listed.

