#### **10.9.6 Cerebrospinal Fluid Safety Lab**

Cerebrospinal fluid safety lab values and changes from baseline over time will be summarized for each continuous clinical laboratory parameter. Shift tables showing the pattern of change from baseline to each postbaseline visit will be presented.

All data will be presented by patient in data listings.

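### Section 10.9 keeps unscheduled laboratory, vital-sign and ECG results out of every table and no worst-postbaseline summary is planned, so the supporting safety tables can understate abnormalities

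*Combined protocol and SAP*

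**What the plan says.** Section 3.1 makes safety primary: "The primary objective of this study is to evaluate the safety and tolerability of WVE-120101 in patients with early manifest HD". Section 3.2 measures it by AEs, their severity, SAEs and withdrawals due to AEs, compared with placebo.

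For the assessment data, Section 10.9 sets one general rule: "Data from unscheduled visits (laboratory tests, vital signs, physical examinations, and ECGs) will not be included in the tables". The same sentence sends these results to listings by patient instead. It gives no exception.

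The individual tables are then described as follows:
- Clinical laboratory (Section 10.9.2): values and changes over time, and "Shift tables showing the pattern of change from baseline to postbaseline visit(s) will be presented".
- CSF safety laboratory (Section 10.9.6): values and changes, and "Shift tables showing the pattern of change from baseline to each postbaseline visit will be presented".
- Vital signs (Section 10.9.3): "The actual value and change from baseline to each postbaseline assessment will be summarized for vital signs".
- ECG (Section 10.9.4): "Summary statistics will be provided for ECG data by dose cohort and visit".

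For late follow-up, Table 1 footnote k says "On Day 196, only platelet count and prothrombin clotting time need to be assessed". Table 2 footnote k says the same of Day 168 in the 32 mg cohort.

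**The concern.** Extra visits are often made because something looks wrong, so results from them are more likely than routine ones to include a patient's extreme value. Leaving them out of by-visit means is ordinary practice and can be defended, since a mean at Day 84 should describe Day 84. The usual counterpart is a second summary that takes each patient's worst postbaseline value from any source. This plan has the exclusion without the counterpart.

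What is at stake is the set of tables a reader uses to see how many patients, by dose and against placebo, moved outside normal or beyond a threshold. A listing shows that a value exists, but it gives no frequency by treatment group.

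**Working it through.** The plan states no figure on this point to reproduce. Its only precision statement (Section 10.2) concerns CSF mHTT and is not an input here. The check is a trace through the text, followed by the visit schedule.

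**1. Where an unscheduled result goes**

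| Data | Planned table | Worst-value or threshold summary | Unscheduled result appears in |
|---|---|---|---|
| Clinical laboratory (10.9.2) | By-visit values, changes, shifts | None stated | Listing; abnormal hematology and chemistry flagged, clinically significant ones listed separately |
| CSF safety laboratory (10.9.6) | By-visit values, changes, shifts | None stated | Unclear: the rule does not name CSF |
| Vital signs (10.9.3) | Values and changes by assessment | None stated | Listing |
| ECG (10.9.4) | Summary by cohort and visit | None stated | Listing |
| Physical examination | No table described | None stated | Listing |

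The one other route into a table is the AE route. Sections 8.2 and 9.1 have abnormal results recorded as AEs when the Investigator considers them clinically significant.

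**2. Scheduled ECG coverage (nominal days)**

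- Table 1 (2 to 16 mg): Screening and Day 28. Multiple-phase doses are on Days 56, 84 and 112. From Day 28 to the end of study on Day 210 is 210 − 28 = 182 days with no scheduled ECG.
- Table 2 (32 mg): Screening, Day 1 (before and after dosing), Day 2 and Day 14. Multiple-phase doses are on Days 28, 56 and 84. From Day 14 to Day 182 is 182 − 14 = 168 days with none.
- Table 3 (treatment-naive patients): Screening only.

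So, as the tables read, any ECG taken after a multiple-phase dose would be unscheduled and kept out of the tables. Treatment-naive patients would contribute no postdose ECG to a table. This depends on column positions in tables extracted from PDF and should be confirmed against the originals.

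**3. Scheduled laboratory coverage**

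Sampling is dense after the first dose: 1, 4 and 24 hours (48 hours in sentinels), then Day 14. From Day 14 the gaps are:
- 2 to 16 mg (Days 14, 28, 56, 84, 112, 140, 196): 14, 28, 28, 28, 28 and 56 days. Table 1 footnote c allows the Week 4 to Week 8 gap to run longer.
- 32 mg (Days 14, 28, 56, 84, 112, 168): 14, 28, 28, 28 and 56 days.

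The last visit at which chemistry is required is Day 140 (Day 112 at 32 mg). Follow-up then continues for 210 − 140 = 70 days (182 − 112 = 70 at 32 mg), out of 14 × 7 = 98 days after the last dose.

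**4. Scale, for illustration only**

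- Sections 4.1 and 6.1 give 9 active patients per cohort. One patient whose abnormality is seen only at an unscheduled visit is 1/9 = 11.1% of that dose group, and the by-visit table would show 0/9.
- Suppose an abnormality lasts d days and starts at a random time in a gap of G days. The chance that no scheduled visit falls within it is 1 − d/G. The durations are assumptions, since the documents give none.

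| d (days) | G = 28 | G = 56 |
|---|---|---|
| 3 | 0.89 | 0.95 |
| 7 | 0.75 | 0.88 |
| 14 | 0.50 | 0.75 |
| 21 | 0.25 | 0.63 |

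These are chances that scheduled visits miss the event. Only if an unscheduled test catches it does the Section 10.9 rule then decide whether it is tabulated.

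**The case against.** The strongest reply is that the primary safety measures are AE counts, and those are not limited to scheduled visits (Section 10.9.1). A marked abnormality is the kind of result an Investigator is most likely to report. Section 9.1 asks for reporting in case of doubt, and Section 9.2.1 grades events by CTCAE. All laboratory data are listed with abnormal hematology and chemistry flagged, about 60 patients make listings readable, and an unblinded Safety Monitoring Committee reviews aggregate safety data (Section 4.3.1). Section 10.1 also defers detail to a SAP, which might add worst-value tables.

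Much of this stands, and it limits the weight of the point. It does not close the gap. AE entry depends on judgment and is not an objective count. The separate listing of clinically significant values covers hematology and chemistry only, with no counterpart for vital signs or ECGs. A SAP that follows Section 10.9 would inherit the exclusion unless it says otherwise.

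A reader might infer more than the documents support:
- That all chemistry after Day 140 (Day 112 at 32 mg) must be unscheduled. Laboratory tests are marked at Day 196 (Day 168), and footnote k sets a minimum. Chemistry drawn at that visit is scheduled data and is not excluded.
- That laboratory tests are only ever four weeks apart. This overlooks the first-dose and Day 14 samples.
- That shift tables for vital signs, examinations or ECGs are affected. Shift tables are planned only for clinical and CSF laboratory data.
- That the 1-in-9 example predicts a result, or can be turned into a contrast of confidence limits. The plan specifies no marked-abnormality count and no such limit, and gives no rate of unscheduled testing.

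**Conclusion.** The point holds as a gap in the supporting safety tables. Followed as written, the plan omits from every assessment table any worst laboratory, vital-sign or ECG value found at an unscheduled visit. A count of patients with abnormalities that leaves out such results can be too low and cannot be too high. ECGs in the multiple-dose phase are the clearest case, followed by chemistry late in follow-up.

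It would be tempting to conclude that the primary safety result is biased. The documents do not support that: the primary endpoint is AE-based and is not directly changed, and unscheduled results are reported, though not tabulated.

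The size cannot be estimated, because nothing indicates how often unscheduled tests will be done or what they will show. The 11 percentage points is the weight of one patient in a group of 9. The conclusion rests on Section 10.9 applying without exception, on no worst-value summary being added elsewhere, and on the ECG rows being read in the right columns. It is a cheap improvement and does not challenge the design.

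**What to change.** Before unblinding, amend Section 10.9 or the SAP as follows:
1. Keep all by-visit summaries and by-visit shift tables on scheduled visits only.
2. Add baseline-to-worst-postbaseline shift tables for laboratory data, using every postbaseline result, scheduled or not.
3. Add counts of patients beyond prespecified thresholds for laboratory, vital-sign and ECG data, on the same basis.
4. Present items 2 and 3 by dose and for placebo.
5. State whether the laboratory tests named in Section 10.9 include the CSF safety laboratory, and give CSF the same scheduled-only and worst-value tables.

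The cost is some SAP wording, a fixed set of thresholds and a few extra tables. The results are already due to appear in the listings, so no new data collection is needed. The downside is that worst-value tables favour detection in patients who are tested more often. Showing the scheduled-only tables beside them lets a reader judge how much of a difference comes from extra testing.

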### **10.9.1 Adverse Events**

Adverse events will be collected and recorded from the time the patient signs the ICF at the Prescreening Visit to the study completion. The verbatim AE term will be coded to the PT and SOC using terminology from the MedDRA.

A TEAE is defined as an AE that is first identified, or is identified to worsen in intensity, at a time point occurring after the first dose of study drug. The numbers and percentages of patients with any TEAE, with any TEAE assessed by the Investigator as related to study drug or to study procedures, and with any treatment-emergent SAE will be summarized by treatment group and overall. Treatment-emergent AEs will be tabulated by relationship to study drug and by severity; these summaries will be presented by SOC and PT, by treatment group and overall. In these tabulations, each patient will contribute only once (ie, the most related occurrence or the most intense occurrence) to each of the incidence rates in the descriptive analysis, regardless of the number of episodes.

All AEs and SAEs occurring during the study (pretreatment, treatment, and follow-up) will be presented by patient in data listings. By-patient listings will also be provided for deaths, SAEs, and AEs leading to study drug discontinuation.

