## **3.2 STUDY ENDPOINTS**

### **Primary Endpoint**

The primary endpoint is the safety and tolerability of WVE-120101, as compared with placebo, as assessed by the number of patients with adverse events (AEs), severity of AEs, number of patients with serious AEs (SAEs), and the number of patients who withdraw due to AEs.

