## **4 STUDY DESIGN**

### **4.1 STUDY DESIGN OVERVIEW**

This is a Phase 1b/2a multicenter, randomized, double-blind, placebo-controlled study to evaluate the safety, tolerability, PK, and PD of IT WVE-120101 in adult patients with early manifest HD who carry a targeted single nucleotide polymorphism, SNP1.

This study will evaluate a single dose of WVE-120101 followed by multiple doses in eligible patients with early manifest HD. To participate in the study, patients must have documented heterozygosity for SNP1 with the thymine (T) variant on the same allele as the CAG triplet expansion. Patients who have not previously undergone SNP analysis will be required to be prescreened to determine heterozygosity for SNP1. The prescreening assessment will have a separate informed consent form (ICF).

Patients may participate in the complete study, in which they will receive all 4 doses. In order to allow for evaluation of a full multi-dose cohort (N=12), new patients may be enrolled directly in the multiple-dose portion to account for those patients who do not roll over from the single-dose portion to the multi-dose portion. These patients will receive 3 doses. Five dose cohorts will be evaluated (2, 4, 8, 16, and 32 mg).

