#### **4.1.5 Follow-up Phase**

All patients are required to complete follow-up assessments, including evaluations of safety, PD, PK, clinical effects, and MRI. Patients will be followed-up for 14 weeks after the last dose (Week 30 for the 2, 4, 8, and 16 mg cohorts and Week 26 for the 32 mg cohort). An early termination (ET) visit will be required in the event of early withdrawal.

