### 5.3.3 Replacements

Patients who drop out before Day 28 (2, 4, 8, and 16 mg cohorts) or Day 14 (32 mg cohort) in the single-dose phase will be replaced in accordance with the requirements for dose escalation. Patients who drop out after this point may be replaced with patients directly entering the multidose part of the study.

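### TEAEs are summarized only as crude percentages of patients who may have had 1, 3 or 4 doses, so comparisons between doses can shift with the dose mix

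*Combined protocol and SAP*

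**What the plan says.** **Summary measure.** Section 10.9.1 plans "The numbers and percentages of patients with any TEAE, with any TEAE assessed by the Investigator as related to study drug or to study procedures", plus treatment-emergent SAEs, with breakdowns by relationship and severity. The counting rule is that "each patient will contribute only once (ie, the most related occurrence or the most intense occurrence) to each of the incidence rates". An event is treatment-emergent if it appears or worsens "at a time point occurring after the first dose of study drug", and no closing day is set. No rate per dose, rate per unit of time or common window is given. Section 10.3.6 summarizes exposure, but separately from adverse events.

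**Use of the counts.** The primary endpoint in Section 3.2 is safety and tolerability "as compared with placebo, as assessed by the number of patients with adverse events (AEs), severity of AEs", SAEs and withdrawals due to AEs. Section 10.9 adds: "Safety data will be analyzed descriptively overall and by treatment group and dose cohort, and no formal statistical comparisons will be performed".

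**Exposure by design.** Full participants receive 4 doses in every cohort. Section 4.1 allows direct entry into the multiple-dose portion: "These patients will receive 3 doses". Under Section 5.3.3, later drop-outs from the single-dose phase "may be replaced with patients directly entering the multidose part of the study". A patient who does not roll over has had 1 dose. Section 4.1.5 ends follow-up 14 weeks after the last dose, at "Week 30 for the 2, 4, 8, and 16 mg cohorts and Week 26 for the 32 mg cohort".

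**The concern.** A crude percentage is comparable between groups when patients have had similar opportunity to show an event. Here the opportunity depends on the number of doses. When a patient leaves after one dose and a direct entrant takes the place, one 4-dose patient becomes two patients, with 1 and 3 doses. The total number of doses is unchanged, but the denominator grows by one and exposure per patient falls. A cohort with many such substitutions can show a lower percentage than a cohort with none at the same underlying risk.

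These percentages are the main display for the primary endpoint and the natural place to look for a dose response. The same problem reaches the placebo comparison if placebo is pooled across cohorts, because the pool then mixes cohorts with different amounts of substitution. The protocol does not say whether it will be pooled.

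**Working it through.** **1. The plan's own figures.** The last dose is on Day 112 (2 to 16 mg) or Day 84 (32 mg), followed by 14 weeks (98 days):
- 2 to 16 mg: (112 + 98)/7 = 30.0 weeks, as stated.
- 32 mg: (84 + 98)/7 = 26.0 weeks, as stated.
- Direct entrants: (210 − 56)/7 = (182 − 28)/7 = 22.0 weeks under either schedule.

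**2. Dose mix, equal risk per dose.** The documents give no adverse event risk and no non-rollover rate, so both are assumptions. With risk p at each dose, independent across doses, the chance of at least one event in k doses is P(k) = 1 − (1 − p)^k. If 3 of 9 active patients stop after one dose and are replaced by direct entrants, 12 patients are counted and the expected crude figure is [6·P(4) + 3·P(1) + 3·P(3)]/12.

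| p | All 9 complete, P(4) | 3 of 9 replaced | Fall (points, from unrounded values) |
|---|---|---|---|
| 5% | 18.5% | 14.1% | 4.5 |
| 20% | 59.0% | 46.7% | 12.3 |
| 30% | 76.0% | 61.9% | 14.1 |

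At p = 20%: P(1) = 20.0%, P(3) = 48.8%, P(4) = 59.0%, so (6 × 0.590 + 3 × 0.200 + 3 × 0.488)/12 = 0.467. With 1, 2 or 4 patients replaced instead of 3, the figure is 54.1%, 50.1% or 43.9%.

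The order of two doses can reverse. At p = 25% with 3 of 9 replaced, P(4) = 68.4%, P(3) = 57.8% and (6 × 0.684 + 3 × 0.250 + 3 × 0.578)/12 = 54.9%. That is below the 59.0% shown by a dose with p = 20% in which everyone completes.

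**3. Dose mix, front-loaded risk.** Assume 30% at a patient's first dose and 5% at each later dose:
- 4 doses: 1 − 0.70 × 0.95³ = 40.0%
- 3 doses: 1 − 0.70 × 0.95² = 36.8%
- 1 dose: 30.0%
- 3 of 9 replaced: (6 × 0.400 + 3 × 0.300 + 3 × 0.368)/12 = 36.7%, a fall of 3.3 points.

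**4. Shorter follow-up at 32 mg.** Under a constant hazard h, the gap between 30 and 26 weeks is exp(−26h) − exp(−30h). It is largest when exp(4h) = 30/26, that is h = 0.0358 per week, where it equals 0.394 − 0.342 = 5.3 points. At 50% incidence by 30 weeks, the 26-week figure is 45.2%, a gap of 4.8 points. One patient in 9 is 11.1 points.

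**5. Patient-time rates.** If events follow doses, 4-dose patients in all cohorts have the same expected number of events, but 32 mg divides by 26 weeks instead of 30. Its rate comes out 30/26 = 1.15 times as high, about 15%, with no true difference.

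**The case against.** - **Placebo is on the same schedule.** It is randomized within each cohort, and under Section 6.1 direct entrants take the treatment of the patient they stand in for. This stands: planned exposure within a cohort is balanced, and a within-cohort bias would need different non-rollover in the two arms. With 3 placebo patients per cohort, however, readers will want a pooled comparison, and dose-to-dose comparisons get no such protection.
- **Risk may be front-loaded.** Section 2.1 reports that most TEAEs so far fell within 28 days of the first dose. This also stands: it weakens any constant-hazard calculation and brings the dose-mix effect down towards step 3. It also favors a table over that same window.
- **The primary endpoint is a number of patients.** At 20% per dose the expected number rises with replacement, from 9 × 0.590 = 5.3 to 12 × 0.467 = 5.6. True, but Section 10.9.1 tabulates percentages too, and here both move with no change in risk.
- **Analyses are descriptive, and detail is left to a SAP.** Section 10.1 does defer to a SAP, and no SAP text on adverse events is in the document reviewed, so the gap may already be filled. Onset dates and by-patient listings would let a reader reconstruct the windows. Even so, descriptive tables are the primary result here, and comparability should not depend on reconstruction from listings.

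**Conclusion.** The point holds as a limited one. Crude percentages are the only planned TEAE summary measure in the protocol, and the design mixes patients with 1, 3 and 4 doses. Comparisons between doses, and with placebo if it is pooled, can be distorted by that mix. The illustrated size with 3 of 9 replaced is 4.5 to 14.1 points at equal risk per dose and about 3 points with front-loaded risk. All of these rest on assumed risks and an assumed number of replacements. With no non-rollover, the dose-mix effect is zero.

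Three stronger readings are not supported:
- **That the comparisons are distorted.** The documents do not give the number of non-continuers or say whether placebo is pooled, so only the possibility is shown.
- **That shorter follow-up at 32 mg hides a dose response.** That cohort has the same 4 doses and the same 14 weeks after the last one. Its schedule is shorter only because the interval after the first dose is 4 weeks instead of 8. The effect is at most 5.3 points.
- **That follow-up runs from 4 to 30 weeks.** Neither end is firm. For patients with a single dose, Section 4.1 gives 4 weeks (32 mg) or 8 weeks (other cohorts), Section 4.3.3 gives 8 weeks if the cohort ends, and Section 4.1.5 gives 14 weeks after the last dose. At the upper end, Table 1 note c lets the interval before multiple dosing lengthen.

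**What to change.** Keep the crude tables and add, by dose cohort and treatment group:

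1. Patients with TEAEs in a common window after the first dose received, closing at 28 days or at the next dose, whichever comes first. Include direct entrants, with the window starting at their own first dose.
2. TEAEs in the multiple-dose phase from its first dose, shown separately for rollover patients and treatment-naive entrants. Combining them would mix first exposures with second ones.

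Patients with an event per dose given, in the same post-dose window, may be added. Patient-year rates should not be relied on, for the reason in step 5.

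State whether placebo is pooled across cohorts for the safety tables. Sections 4.1, 4.1.5 and 4.3.3 on follow-up of patients who receive only the single dose must be reconciled.

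The cost is some SAP wording and a few tables from dose and onset dates already collected. The downside is more tables with small counts: with 9 active and 3 placebo patients per cohort, the split in item 2 will leave some cells nearly empty.
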